During the treatment period, patients will have weekly in-clinic visits through week 4, and then in-clinic visits Q4W through week 16 with weekly telephone visits in between the in-clinic visits. Parents/caregivers will be trained on injecting study drug during in-clinic visit 3 (day 1), visit 5 (week 2), and visit 7 (week 4) (this only applies to patients who will receive Q2W treatment during the study). During weeks in which no in-clinic visit is scheduled, the parent/caregiver will administer study drug to the patient. In case the parent/caregiver does not want to administer study drug to patient, they may have the clinic staff administer all the study drug injections in the clinic. Safety, laboratory, and clinical assessments will be performed at specified clinic visits, as noted in Appendix 10.2. The end of treatment period visit will occur at week 16, two weeks after the last dose of study drug for patients randomized to the Q2W treatment group or placebo Q2W group, and 4 weeks after the last dose of study drug for patients randomized to the Q4W treatment or placebo Q4W group. The co-primary endpoints will be assessed at this visit. If patients prematurely discontinue study treatment, the patients will be encouraged to stay in the study to have data collected at all remaining scheduled visits until completion of the planned end of study visit. Patients who participate in the study may subsequently be eligible to participate in an OLE study. All patients will be offered the opportunity to screen for entry into the OLE study at the end of the treatment period (week 16).

Patients who decline to enroll in the OLE study or those who fail eligibility criteria for the OLE study will have a 12-week follow-up period. For these patients, after week 16, follow-up visits will occur every 4 weeks from week 20 to week 28. During the follow-up period, patients will be monitored for safety and tolerability and have laboratory and clinical assessments as noted in Appendix 10.2.

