Rescue treatments (i.e. both medications and procedures): If medically necessary (i.e. to control intolerable AD symptoms), rescue treatment for AD may be provided to study patients at the discretion of the investigator. Investigators will be required to perform an IGA assessment prior to starting rescue treatment and initiate rescue treatment only in patients who either have an IGA score = 4 or have intolerable symptoms. If possible, investigators are encouraged to consider rescue initially with topical treatment (e.g., high potency TCS) and to escalate to systemic medications only for patients who do not respond adequately after at least 7 days of topical treatment. Patients may continue study treatment if rescue consists of topical medications.

Patients who receive systemic corticosteroids or systemic non-steroidal immunosuppressive drugs (e.g., cyclosporine, methotrexate, mycophenolate-mofetil, azathioprine, etc.) as rescue medication during the study will be discontinued permanently from the study drug. All patients will be asked to complete the scheduled study visits and assessments whether or not they complete study treatment and whether or not they receive rescue treatment for AD. Investigators should make every attempt to conduct efficacy and safety assessments (e.g., disease severity scores, safety laboratory tests) immediately before administering any rescue treatment. An unscheduled visit may be used for this purpose, if necessary. For the purpose of efficacy analysis, patients who receive rescue treatment during the study will be considered treatment failures.

Blinded adjudication of rescue treatments will be implemented before database locks by considering the type of medication or procedure, indication, timing, frequency and the potential impact of the use of the prohibited medication or procedure. The rescue treatments will be adjudicated by the clinical study director and the adjudication procedure will be documented.

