4.4.2. Secondary Efficacy Variables

The key secondary endpoints are:

- Proportion of patients with EASI-75 ($\geq 75\%$ improvement from baseline) at week 16 (this is not a secondary endpoint for ex-US countries as it is already a co-primary endpoint)
- Percent change in EASI score from baseline to week 16
- Percent change from baseline to week 16 in weekly average of daily worst itch score

Worst itch scale

The worst itch scale is a simple assessment tool that patients will use to report the intensity of their pruritus (itch). This tool is composed of two questions and each question is an 11-point scale (0 to 10) in which 0 indicates no itching while 10 indicates worst itching possible. Patients will be asked the following 2 questions:

- “What was the worst itch you had today?”
- “What was the worst itch you had last night?”

Patients will be asked to provide answers to these 2 questions daily throughout the entire study (screening period, treatment period, and follow-up period; see time point in [Appendix 10.2](#)). The daily worst itch score will be calculated as the worse of the scores for the 2 questions on a given day. Any day with one score only should be discarded as a “missing score day”.

Patients will be instructed on using the patient diary to record their worst itch score at the screening and baseline visits. Clinical sites will check and remind patients to complete the diary at each visit.

The baseline worst itch scale score is defined as the prorated average of the worst itch scale scores reported continuously for 7 days right before the baseline visit (i.e. study day -7 to day -1). A minimum of 4 daily scores out of the 7 days is required to calculate the baseline average score. For post-baseline worst itch scale score, the weekly mean of daily worst itch score is calculated as the prorated average of the reported daily worst itch score within the week. For example, if there are 3 scores in a week, the prorated average = $(\text{score1} + \text{score2} + \text{score3})/3$.

Other secondary endpoints are:

- Change from baseline to week 16 in weekly average of daily worst itch score
- Proportion of patients with EASI-50 at week 16
- Proportion of patients with EASI-90 at week 16
- Change from baseline to week 16 in percent BSA affected by AD
- Percent change from baseline to week 16 in SCORAD
- Proportion of patients with improvement (reduction) of weekly average of daily worst itch score ≥ 4 from baseline at week 16

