5.7.2. Analyses of Secondary Efficacy Variables

All secondary endpoints will be evaluated on the FAS. Selected secondary endpoints will be evaluated in the mFAS as sensitivity analyses.

The binary secondary efficacy endpoints will be analyzed using the same approaches used for the analysis of the primary endpoints.

The continuous endpoints will be analyzed using analysis of covariance (ANCOVA) model as the primary analysis method with multiple imputation (MI) method for missing data. Patients' efficacy data through week 16 after the rescue treatment use will be set to missing first, and then be imputed by MI method. To account for the uncertainty in the imputation, missing data from the FAS will be imputed 40 times to generate 40 complete data sets by using the SAS procedure MI following the 2 steps below:

Step 1: The monotone missing pattern is induced by Markov Chain Monte Carlo (MCMC) method in MI procedure using seed number 12345. The monotone missing pattern means that if a patient has missing value for a variable at a visit, then the values at all subsequent visits for the same variable are all missing for the patient.

Step 2: The missing data at subsequent visits will be imputed using the regression method for the monotone pattern with seed number 54321 and adjustment for covariates including treatment groups, randomization strata (baseline weight group and region), and relevant baseline.

Once imputations are made, the week 16 data of each of the 40 complete datasets will be analyzed using ANCOVA model with treatment, randomization strata (baseline weight group and region), and relevant baseline included in the model, and the SAS MIANALYZE procedure will be used to generate valid statistical inferences by combining results from the 40 analyses using Rubin's formula.

The imputation model will include:

- The covariates included in the ANCOVA model, including the treatment group, the baseline value and the randomization strata (baseline weight group and region)
- Measured endpoint values at every clinic visit (i.e. week 1, 2, 3, 4, 8, 12 and week 16)

Categorical variables included in above model (i.e., treatment group and randomization strata) are not expected to be missing.

To account for the impact of rescue treatment on the efficacy effect:

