- Continuous efficacy endpoints: if a patient receives rescue treatment that specifies the patient as a non-responder according to the above rules for binary efficacy endpoints, the data collected after rescue treatment is initiated will be treated as missing.

Sensitivity analyses

In addition to the MI method described previously, sensitivity analyses for the continuous endpoints for EASI and/or Pruritus worst itch scale will be conducted as described below.

1. The sensitivity analysis based on all observed data regardless if rescue treatment is used or data is collected after withdrawal from study treatment using MI method will be performed.
2. This sensitivity analysis will use ANCOVA model, including the treatment group, the baseline value and the randomization strata. The efficacy data will be set to missing after rescue treatment is used. The post-baseline LOCF method will then be used to impute missing values.
3. This sensitivity analysis will use ANCOVA model, including the treatment group, the baseline value and the randomization strata. The efficacy data will be set to missing after rescue treatment is used. The post-baseline worst observation carried forward (WOCF) method will then be used to impute missing values.

Time to onset of effect on pruritus as measured by proportion of patients with improvement (reduction) of weekly average of daily Pruritus worst itch scale ≥ 4 and ≥ 3 from baseline during the 16-week treatment period will be calculated for each patient as the date of having the first event - the first study drug dose date + 1 day. Patients not having either event during the treatment period will have their time censored at the end of treatment period. These times to onset of effect on pruritus will be analyzed using the Cox proportional hazards model including treatment and randomization strata as factors, The hazards ratio, its 95% confidence interval and p-value will be reported. Kaplan-Meier curves will be provided.

The mean weekly dose of TCS use during the treatment period endpoints will be analyzed using an ANCOVA model with treatment, randomization strata (baseline weight group and region) and relevant baseline included in the model.

Analysis of incidence of TEAE-related variables

- Incidence of skin infection TEAE (excluding herpetic infections) from baseline through week 16
- Incidence of treatment-emergent serious adverse events from baseline through week 16

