6.4. Analysis Visit Window

Data analyzed by-visit-analysis (including efficacy, laboratory data, visit sign, ECG, ADA) will be summarized by the study scheduled visits described in the study protocol and SAP "Schedule of Events". The analysis visit windows will be exhaustive so that all available values obtained from unscheduled visits, early termination (ET) visit and end of treatment (EOT)/end of study (EOS) have the potential to be summarized. No analysis visit windows will be applied for the study scheduled visits.

The following analysis visit windows will be used to map the unscheduled visits, ET and EOT/EOS visits, based on the study day:

Visit	Target Day	Analysis Time Window Based on Study day*
Screening	<1	<1
Baseline	1	1
Week 1	8	[2,11]
Week 2	15	[12,18]
Week 3	22	[19,25]
Week 4	29	[26, 43]
Week 8	57	[44, 71]
Week 12	85	[72, 99]
Week 16	113	[100, 127]
Week 20	141	[128, 155]
Week 24	169	[156, 183]
Week 28	197	>=184

*study day is calculated relative to the date of first study drug injection.

In general, the following order will be used to select the record for analysis at given visit:

1. Scheduled visit
2. Early termination (ET) or end of study (EOS), whichever comes first if scheduled visit not available
3. Unscheduled visit if both scheduled visit and ET/EOT/EOS are not available

For the multiple measurements of the same test in the same window, the following rules will be used to pick up the analysis value:

- If multiple valid values of a variable within an analysis visit window, the closest from the target study day will be selected.
- If the difference is a tie, the value after the targeted study day will be used.
- If multiple available values of a variable exist within a same day, then the first value of the day will be selected.

Both scheduled and unscheduled measurements will be considered for determining abnormal/PCSV values from laboratory, vital sign or ECG as well as the baseline values.

For the daily collected ePRO data, the analysis visit windows will be implemented following the procedure below:

Step 1: Derive the study day,

- If diary date \geq 1st injection date, then diary study day=diary date – 1st injection date +1;
- Otherwise diary study day=diary date – 1st injection date

Step 2: Windows are defined as diary study day -7 to -1 = BL, 1 to 7 = week 1, 8 to 14 = week 2, etc, with 7 days interval between visit windows.

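### For worst itch, the imputation model uses clinic-visit weeks only and leaves out 9 of the 15 weekly averages before week 16; the effect is nil to small and the remedy is inexpensive

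*SAP*

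**What the plan says.** SAP 5.7.2 imputes missing continuous data 40 times. An MCMC step makes the missing pattern monotone, and a sequential regression over visits then fills the rest. Besides the ANCOVA covariates, the model holds "Measured endpoint values at every clinic visit (i.e. week 1, 2, 3, 4, 8, 12 and week 16". No other list is given for diary endpoints. Protocol 10.5.2.2 describes the same two steps without naming weeks.

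Worst itch is collected differently. SAP 4.4.2 states: "Patients will be asked to provide answers to these 2 questions daily throughout the entire study". After baseline, "the weekly mean of daily worst itch score is calculated as the prorated average of the reported daily worst itch score within the week". SAP 6.4 gives the diary its own windows: "Windows are defined as diary study day -7 to -1 = BL, 1 to 7 = week 1", and so on in 7-day steps. After week 4 the schedule has "in-clinic visits Q4W through week 16 with weekly telephone visits in between the in-clinic visits" (SAP 2.3).

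SAP 4.3 tells investigators to "initiate rescue treatment only in patients who either have an IGA score = 4 or have intolerable symptoms". Efficacy should be assessed just before rescue: "An unscheduled visit may be used for this purpose, if necessary". For continuous endpoints, "the data collected after rescue treatment is initiated will be treated as missing" (SAP 5.7.2).

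**The concern.** Multiple imputation under missing at random should condition on observed data that predict both missingness and the outcome. Recent itch plausibly predicts both rescue and week 16 itch. If rescue starts between clinic visits, the last averages before rescue are observed but unused. With rescue at an unscheduled visit in week 15, for example, the model stops at week 12 and ignores weeks 13 and 14. A patient who lacks only the week 16 average has weeks 13-15 ignored.

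At stake is the estimate for a key secondary endpoint, percent change in worst itch, and for change in worst itch. The binary itch endpoints use the non-responder rule and are untouched, as is EASI.

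**Working it through.** **1. The plan's list.** The in-clinic visits after baseline in SAP Appendix 10.2, Table 1 are V4, V5, V6, V7, V11, V15 and V19, at weeks 1, 2, 3, 4, 8, 12 and 16. This reproduces the SAP's list.

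**2. The count for itch.** Weeks 1 to 15 give 15 averages before week 16. Six are listed (1, 2, 3, 4, 8, 12), so 15 - 6 = 9 are not (5, 6, 7, 9, 10, 11, 13, 14, 15).

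**3. When the omission can matter.** Diary week w covers days 7(w - 1) + 1 to 7w. Week 8 is days 50-56 and its clinic visit is day 57; week 12 is days 78-84 and its visit is day 85. Rescue started at a scheduled visit on its target day therefore follows an average that is already in the model. The 3-day visit window blurs this slightly.

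**4. Information about week 16.** Correlations are assumed. For a pure AR(1) process with weekly correlation r and last used week L, R-squared = r^(2(16 - L)). The listed model uses the last listed week at or before the last observed week.

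| Last observed week | r = 0.90, listed / all weeks | r = 0.98, listed / all weeks |
|---|---|---|
| 4, 8 or 12 | no difference | no difference |
| 7 | 0.08 / 0.15 | 0.62 / 0.70 |
| 11 | 0.19 / 0.35 | 0.72 / 0.82 |
| 15 | 0.43 / 0.81 | 0.85 / 0.96 |

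For example, 0.90^8 = 0.43 from week 12, and 0.90^2 = 0.81 from week 15.

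**5. Effect on the treatment difference.** All inputs other than the 110 per arm and the listed weeks are assumed.

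*Two-arm simulation* (true difference 2 itch points, SD 2, random intercept plus AR(1) 0.9, 20 imputations, 150 runs):
- Rescue in weeks 1-4, 20% placebo and 5% active: -2.019 listed, -2.017 all weeks.
- The same rates, spread evenly over weeks: -2.005 and -2.002.
- Rescue driven by the current week's itch, 10% placebo and 4% active: -1.978 and -1.994. The gap is 0.016 (0.016/1.994 = 0.8%; 0.016/0.227 = 0.07 SE).
- The same, 19% and 8%: -1.903 and -1.933. The gap is 0.030 (0.030/1.933 = 1.6%; 0.030/0.236 = 0.13 SE).

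*Three-arm simulation* (true differences 28 points for Q2W and 25 for Q4W; AR(1) 0.75 with SD 22, random intercept and slope SD 12 each; 40 imputations, 4000 trials). The figures are Q2W bias toward zero against the full-data ANCOVA, with listed weeks:
- Rescue can follow any week's itch, 15% placebo and 6% Q2W: 0.51 (0.51/28 = 1.8%).
- The same, 30% and 13%: 0.95 (3.4%; 0.95/4.21 = 0.23 SE).
- Half of patients rescued only at clinic visits, 30% and 15%: 0.54 (1.9%).
- Clinic visits only, 16%/8% to 50%/32%: -0.03 to 0.03 over both regimens.
- All weeks in the model: at most 0.03 in these runs (simulation error 0.02-0.05).

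*The SAP's two-step method* with 10% of weekly averages missing and 30% placebo rescue. Listed minus all weeks, Q2W, was 0.98 (error 0.05; 3.5%; 0.22 SE; 617 trials) when rescue could follow any week. It was 0.03 (error 0.04; 706 trials) when rescue was confined to clinic visits.

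*Rescue only partly driven by itch.* This is a large-sample check with the same covariance values and about 25% placebo rescue. The bias was 0.87 (3.1%) when rescue followed itch itself, 0.50 (1.8%) when it followed a score correlated 0.6 with itch, and 0.39 (1.4%) at 0.4.

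**6. Power and precision.** In the three-arm simulation, power is at least 99.9% with either model. Total squared error about the true difference, listed against all weeks, is between 1% smaller and 3% larger at 15-30% placebo rescue.

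**The case against.** The listed model is workable and pre-specified, and its effect may be nil. Rescue requires an IGA assessment and either IGA 4 or intolerable symptoms, so it need not track itch closely, and the attenuation falls when it does not. The list is plainly generic: CDLQI, POEM, DFI and PROMIS are not scheduled at weeks 1 and 3, so a programmer must adapt it anyway and might do so for itch. The LOCF and WOCF sensitivity analyses can pick up weekly averages between clinic visits. No minimum number of diary days applies after baseline, so some added averages may be poorly supported.

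Most of this stands, and it is why the point is optional. Two parts do not remove it. The SAP exists to pre-specify, and it does not say that the list is adapted for itch. LOCF, WOCF and the all-observed analysis change the assumptions about missing or post-rescue data. None of them fits the primary model with all weeks, and they are promised for EASI and/or itch, so possibly not for itch.

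**Conclusion.** The omission is certain from the text: 9 of 15 averages. Its effect is nil to small. There is none if rescue starts only at scheduled clinic visits. There is roughly 1-3% attenuation, about 0.1-0.2 SE, if rescue follows bad itch between visits, is commoner on placebo and reaches about 10-30% there. These figures depend on assumed rescue rates, timing and correlations that the documents do not give.

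Three stronger readings might be inferred, and the documents support none of them.
- **60% of the information is lost.** Neighbouring weeks are correlated, and the table above shows no loss when the last observed week is 4, 8 or 12.
- **The difference is attenuated by up to 6%.** That figure (1.72/28 = 6.1%) needs 49% placebo rescue driven by itch alone.
- **The model can bias away from zero or inflate type I error.** The bias reversed (about 3%) only when missingness followed good itch at 30% placebo and 16% Q2W, which is implausible for rescue under the rule in SAP 4.3. With no true difference, that case gave rejection of 5.5% (Q2W) and 5.4% (Q4W) with listed weeks against 4.6% for both with all weeks (error about 0.35 points), which is not meaningful inflation.

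No direction, change in decision or loss of power is claimed.

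**What to change.** In SAP 5.7.2, name the weeks by endpoint:
- Percent change and change in worst itch: all weekly averages from week 1 to week 16. Check convergence of the MCMC step, and keep the listed clinic-visit model as the stated fallback if it does not converge.
- EASI, SCORAD, BSA and GISS: weeks 1, 2, 3, 4, 8, 12 and 16, as now.
- CDLQI, POEM, DFI and PROMIS: the scheduled weeks 2, 4, 8, 12 and 16.

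The cost is SAP wording and minor programming, with no new data; the weekly averages are already needed for the time-to-onset endpoints. The change should be made before database lock and before any unblinded first-step analysis.

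The downside is 16 instead of 7 correlated variables in the MCMC step, a longer run (about 5 times per iteration in a test), and some averages that rest on few diary days. In that test, with 10% random weekly gaps, convergence was as good with 16 variables as with 7 (maximum R-hat 1.002 against 1.008).

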### 7.3. Rescue Treatment

Rescue treatment for AD may be provided to patients during the study. Investigators will be required to perform an IGA assessment prior to starting rescue treatment and initiate rescue treatment only in patients who either have an IGA score = 4, or have intolerable symptoms. If possible, investigators are encouraged to consider rescue initially with topical treatment (eg, high-potency TCS) and to escalate to systemic medications only for patients who do not respond adequately after at least 7 days of topical treatment. Patients may continue study treatment if rescue consists of topical medications. The use of very-high-potency or superpotent TCS is prohibited in this study, even as rescue treatment, as their use is not recommended in patients under 12 years of age. Very-high-potency topical corticosteroids include:

- Betamethasone dipropionate augmented 0.05% ointment
- Clobetasol propionate 0.05% solution, foam, cream or ointment
- Diflorasone diacetate 0.05% ointment
- Halobetasol propionate 0.05% cream or ointment

Patients who receive systemic corticosteroids or systemic non-steroidal immunosuppressive drugs (eg, cyclosporine, methotrexate, mycophenolate-mofetil, azathioprine, etc) as rescue medication during the study will be discontinued permanently from the study drug. All patients will be asked to complete the scheduled study visits and assessments whether or not they complete study treatment and whether or not they receive rescue treatment for AD. Investigators should make every attempt to conduct efficacy and safety assessments (eg, disease severity scores, safety laboratory tests) immediately before administering any rescue treatment. An unscheduled visit may be used for this purpose, if necessary. For the purpose of efficacy analysis, patients who receive rescue treatment during the study will be considered treatment failures.

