5.7.1. Analysis of Primary Efficacy Variable

The Cochran-Mantel-Haenszel (CMH) test adjusted by randomization strata (baseline weight group (<30 kg or ≥30kg) and region (North America or Europe) will be used for the analysis of percentage of patients with IGA 0 or 1 at week 16 or percentage of patients with EASI-75 at week 16. The Mantel-Fleiss (MF) criterion will be performed, and if it is not met while using the option CMH (MF) in SAS procedure PROC PREQ, sensitivity analyses including each factor separately in CMH test will be conducted.

All efficacy data, regardless of whether the patient remains on study treatment or discontinues the study treatment but remains in the study, will be used for analysis. Specifically, if a patient stays in the study until the end of the study planned placebo-controlled treatment period, all efficacy data collected up to the study planned end of treatment visit will be included in the primary analysis, regardless of whether the patient is on treatment or not.

Handling of dropouts or adjudicated rescue treatment or missing value for the binary response variables as the primary analysis

- If a patient withdraws from the study, this patient will be counted as a non-responder for the time points after withdrawal.
- To account for the impact of rescue treatment on the efficacy effect: if rescue treatment is used (see Section 4.3 for rescue treatment), the patient will be specified as a non-responder from the time the rescue treatment is used.
- If the patient has the missing value at week 16, then it will be counted as a non-responder at week 16.

Sensitivity analyses

1. Post-baseline Last Observation Carried Forward (LOCF) approach after censoring for rescue treatment use or study withdrawal to determine patient's status at week 16 will be conducted to assess the robustness of the primary efficacy analysis with regards to handling of missing data.
2. All observed data, regardless if rescue treatment is used or data is collected after withdrawal from study treatment will be included for analysis. Patients with missing value will be counted as non-responder.

The primary efficacy analyses will be performed on the FAS, which will be considered as the primary analysis. Evaluation of primary and co-primary endpoints in the mFAS and PPS will be considered as sensitivity analyses.

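### Does the time-to-itch-onset analysis count relief first reached after rescue as onset?

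*SAP*

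**What the plan says.** SAP 5.7.2 describes the two onset endpoints "as measured by proportion of patients with improvement (reduction) of weekly average of daily Pruritus worst itch scale" at the two thresholds. The time is "calculated for each patient as the date of having the first event", less the first dose date, plus one day. The censoring rule is: "Patients not having either event during the treatment period will have their time censored at the end of treatment period". A Cox model with treatment and randomization strata follows, with hazard ratio, 95% confidence interval, p-value and Kaplan-Meier curves. Protocol 10.5.2.2 and SAP Appendix 10.1 add no rescue rule for this endpoint type.

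Rescue is dealt with in three other places:

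- **General rule.** Protocol 7.3: "For the purpose of efficacy analysis, patients who receive rescue treatment during the study will be considered treatment failures". SAP 4.3 repeats it: "patients who receive rescue treatment during the study will be considered treatment failures".
- **Binary endpoints.** SAP 5.7.1: "the patient will be specified as a non-responder from the time the rescue treatment is used". SAP 5.7.2 extends this: "The binary secondary efficacy endpoints will be analyzed using the same approaches used for the analysis of the primary endpoints". That covers the binary itch responses at the same two thresholds.
- **Continuous endpoints.** SAP 5.7.2: "the data collected after rescue treatment is initiated will be treated as missing".

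**The concern.** The detailed rescue rules are labelled for binary and continuous endpoints, and time-to-event is a third type with no rule of its own. If the onset paragraph is programmed exactly as it stands, a child who is rescued in week 6 and first reaches the threshold in week 8 has an onset at week 8. The same child is a non-responder in the week 16 proportion at that threshold. The curve and the proportion would then describe different things, and the onset curve would partly show the effect of rescue medication.

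Both are named secondary endpoints, so the hazard ratio would appear in the study report. No sensitivity analysis is listed for the onset endpoints that would expose the difference. Two programmers who read the plan differently could report different hazard ratios.

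**Working it through.** **Step 1: what each rule does to a rescued child with no onset before rescue.**

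1. *General failure rule (SAP 4.3, Protocol 7.3).* It applies to efficacy analysis and is not limited by endpoint type. Time to itch onset is listed among the secondary efficacy variables in SAP 4.4.2, so the rule reaches it. A failure has no onset afterwards. The onset paragraph's own censoring sentence then carries the child to the end of treatment.
2. *Binary rule (SAP 5.7.1 and 5.7.2).* Non-response starts at the time of rescue, so the status is indexed by time and can be applied to a first-event date. The onset paragraph itself refers to the proportion of patients improved. The result is again a non-event to the end of treatment.
3. *Continuous rule (SAP 5.7.2).* Weekly itch after rescue is missing and cannot supply a qualifying week. The imputed datasets are analysed by ANCOVA, not by the Cox model. The result is the same.
4. *Onset paragraph alone.* Onset can occur after rescue. This needs SAP 4.3 to be set aside.

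An onset before rescue is kept under all four. Censoring at the rescue date is not written anywhere in the plan; the only censoring time given is the end of treatment.

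**Step 2: how far the reading could move the estimate.** The plan has no figure to reproduce. The documents give no itch-onset, rescue or post-rescue relief rates, so everything here is assumed. The EASI-75 planning rates in SAP 2.2 stand in for 16-week itch onset: 17% placebo and 62% or 68% dupilumab.

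Without rescue and with exponential onset, HR = ln(1 − p_dupilumab) / ln(1 − p_placebo):

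- 68%: ln 0.32 / ln 0.83 = 1.139 / 0.186 = 6.1
- 62%: ln 0.38 / ln 0.83 = 0.968 / 0.186 = 5.2

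Weekly times with Breslow ties bring these to 5.95 and 5.06 in simulation. Rescue is then placed uniformly over weeks 2 to 12, and a share q of rescued children reach the threshold 1 to 4 weeks later. Hazard ratios for 17% against 68%:

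| Rescue, placebo / dupilumab | q | Non-event to week 16 | Censored at rescue | Onset paragraph alone |
|---|---|---|---|---|
| none | – | 5.95 | 5.95 | 5.95 |
| 3% / 1% | 20% | 6.00 | 5.95 | 5.77 |
| 10% / 3% | 20% | 6.15 | 5.96 | 5.41 |
| 20% / 5% | 0% | 6.46 | 5.99 | 5.95 |
| 20% / 5% | 40% | 6.45 | 5.99 | 4.26 |
| 30% / 10% | 60% | 6.61 | 5.99 | 3.16 |
| 20% / 20% | 40% | 5.77 | 5.95 | 4.47 |

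With 62% in place of 68%, the 30% / 10%, q = 60% row gives 5.66, 5.11 and 2.71.

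Across the scenarios with 10–30% placebo rescue and q of 20–60%, the placebo onset rate moves from 16.1% to 18.7% at the least and from 14.2% to 31.9% at the most. Per 110 children that is 110 × 0.026 = 2.9 to 110 × 0.177 = 19.5 on placebo. On dupilumab about 1 to 6 children change status.

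Two features matter. The non-event value exceeds the no-rescue value when rescue is commoner on placebo, so part of the drop from 6.45 to 4.26 comes from that starting point; from censoring at rescue the drop is 5.99 to 4.26. And when q = 0 the isolated reading returns the no-rescue hazard ratio and almost matches censoring.

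**Step 3: what depends on it.** The 22-step hierarchy in SAP 5.7.2 contains the binary itch responses at 4 points (steps 6 and 12) and 3 points (steps 13 and 15), which have an explicit rescue rule. The onset endpoints are not in it.

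**The case for a change.** The strongest reply is that calling someone a treatment failure states an intent and does not give an event rule. The SAP did not rely on that sentence for binary or continuous endpoints, where it wrote the rule out, so its silence on the third type leaves a choice. The gap between readings also survives equal rescue in the two arms (5.77 against 4.47 at 20% each with q = 40%).

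Part of this stands. The cross-reference is absent, and one sentence applying the existing rescue rule to the onset endpoints would be harmless. If rescue is common and works quickly, the isolated reading would differ materially from the others.

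It does not follow that the plan leaves the answer open. Every rescue rule that the SAP does write leads to one result once joined to the censoring sentence. The contrary reading requires one paragraph to be separated from the rest of the document. The expected analyst behaviour is to apply the binary rule.

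An added analysis censoring at rescue is a matter of preference. Rescue is limited to children with IGA 4 or intolerable symptoms, so that censoring would probably be informative.

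**Conclusion.** No change follows. The onset paragraph lacks a cross-reference that analysts can supply from SAP 4.3, 5.7.1 and the rest of 5.7.2: improvement first reached after rescue is not an onset, and a rescued child without earlier onset stays a non-event to the end of treatment.

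The possible shift in the hazard ratio runs from almost nothing to roughly half, depending entirely on assumed onset, rescue and relief rates that the documents do not contain. In the scenarios with 10–30% placebo rescue and added relief after rescue, the isolated reading works against dupilumab, so it would not flatter the drug. No alpha-controlled test, stated power or sample size depends on the point. The conclusion rests on reading the general failure statement as covering all listed efficacy endpoints, which is what its wording says.
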